## NUMBER OF PLATELET TRANSFUSIONS

The incidence of platelet transfusions will be monitored by the investigator (or appropriately delegated study site personnel) from randomization. The number of transfusions administered (if used), along with date and start/stop times, will be specified and recorded in the CRF. In order to minimize missing data for the primary endpoint, “Not Done” (or “Not Applicable”) will be collected on the CRF to indicate subjects who did not receive a platelet transfusion.

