5.1 STUDY ENDPOINTS

5.1.1 Primary Endpoint(s)

The primary efficacy endpoint is the proportion of subjects who do not require a platelet transfusion or any rescue procedure for bleeding after randomization and up to 7 days following an elective procedure.

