5.2 STUDY SUBJECTS

5.2.1 Definitions of Analysis Sets

Full Analysis Set (FAS): The FAS is the group of all subjects who are randomized into the study.

Per Protocol Analysis Set (PP): The PP is the group of all randomized subjects who receive protocol-assigned study drug and do not meet any of the following criteria:

- Baseline platelet count of $>50 \times 10^9/L$
- Subjects who were enrolled in the study despite not being planned for transfusion even in the event of no significant increase of platelet count
- Taking prohibited prior medications or prior transfusion
- Presence of significant bleeding at baseline
- Did not have a protocol permitted procedure on Day 8 - 15
- Received dose different from the intended dose
- Received $<80\%$ of the total dose or received $>40\%$ of total dose without food
- No elective procedures or elective procedure outside day 8-15
- Subject received platelet transfusion before knowing V4 platelet count
- Subject refused platelet transfusion

Subjects who met any of the criteria listed above will be excluded from the PP due to possible introduction of bias.

Safety Analysis Set: The Safety Analysis Set is the group of subjects who receive at least one dose of study drug and have at least one post dose safety assessment.

The number (percentage) of subjects in each analysis set will be summarized by treatment groups using descriptive statistics. The summaries for FAS and PP will be based on subjects “as randomized”. The summary for Safety Analysis Set will be based on subjects “as treated”.

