5.3.2 Adjustments for Covariates

The primary efficacy endpoint, the proportion of subjects without platelet transfusion or any rescue procedure for bleeding, and the first secondary efficacy endpoint, proportion of subjects with platelet count $\geq 50 \times 10^9/L$ on Procedure Day, will be analysed separately within each

baseline platelet count cohort ($<40 \times 10^9/L$ or from 40 to $<50 \times 10^9/L$) using the Cochran-Mantel-Haenszel (CMH) test adjusting for the risk of bleeding associated with the elective procedure (low, moderate, or high based on Amendment 02 categorization). Since the HCC status is included in the randomization stratification for safety purposes only, not for efficacy consideration, HCC will not be included in the CMH model for the primary efficacy analysis.

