5.4.1.1 Sensitivity Analysis

The following analyses will be considered as sensitivity analyses:

- PP analysis: The same primary efficacy analyses described in [Section 5.4.1](#) will be repeated based on the PP analysis set.
- Observed case: The same primary efficacy analyses described in [Section 5.4.1](#) will be repeated based on observed data. Subjects with missing information about the primary efficacy outcome will be excluded from this analysis.
- Fisher's exact Test: The same primary efficacy analyses described in [Section 5.4.1](#) will be carried out using Fisher's exact test.
- Modified primary efficacy endpoint: Proportion of subjects who do not require a platelet transfusion after randomization and up to 7 days following an elective procedure. This efficacy endpoint will be analyzed using the same approach as primary efficacy analysis using FAS

Additional sensitivity analyses may also be explored, if deemed appropriate.

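### The per-protocol set is selected on a component of the primary endpoint, so the PP sensitivity analysis has a bias of unknown sign in the treatment difference

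*SAP*

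**What the plan says.** The primary endpoint (SAP 5.1.1) is the proportion of subjects who "do not require a platelet transfusion or any rescue procedure for bleeding after randomization", up to 7 days after the procedure. Any platelet transfusion in that window is a failure.

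The PP list in SAP 5.2.1 includes two transfusion criteria: "Subject received platelet transfusion before knowing V4 platelet count" and "Subject refused platelet transfusion". The reason given for the whole list is: "Subjects who met any of the criteria listed above will be excluded from the PP due to possible introduction of bias". SAP 7 records that the PP criteria were finalised in version 3.0. The protocol's own PP definition (9.7.1.2) names neither criterion; it lists major violations, prohibited medication and noncompliance.

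SAP 5.4.1.1 makes the PP set the basis of a named sensitivity analysis: "PP analysis: The same primary efficacy analyses described in" Section 5.4.1 are repeated on it.

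On scoring, SAP 5.3.2 describes the outcome as "the proportion of subjects without platelet transfusion or any rescue procedure for bleeding", and in Protocol 9.5.1.3 a 'Not Done' or 'Not Applicable' entry "will be collected on the CRF to indicate subjects who did not receive a platelet transfusion". Neither document has an explicit rule for a subject who is offered platelets and declines.

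**The concern.** A per-protocol set should be defined by adherence, not by outcome. Here one criterion is an endpoint event and the other is closely tied to one.

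The early-transfusion criterion does not ask why the platelets were given. Protocol 9.5.1.3 lists platelet transfusion among the rescue procedures for bleeding, and Protocol 9.4.7.2 permits rescue therapy for bleeding. A subject who takes every dose, bleeds on Day 6 and receives platelets has kept to the protocol and is a true failure, yet leaves the PP set.

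At stake is the value of the PP analysis as a robustness check. If the set is selected partly on the outcome, agreement with the FAS is weaker support than it appears, and disagreement is hard to interpret.

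**Working it through.** **Inputs.** SAP 4 gives 18% response on placebo, a difference of 35 points (so 53% on avatrombopag), and 67 v 33 subjects per cohort. The documents give no counts of early transfusions or refusals, so the shares below are assumptions, taken from 0 to 10%.

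**The plan's own figure.** Exact enumeration of the two-sided Fisher test at 0.05, with 67 subjects at 53% and 33 at 18%, gives 92.6% power. This agrees with the stated figure of more than 90%.

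**Early-transfusion criterion.** Let f be the share of an arm removed. All are failures, so the responders stay and the denominator shrinks: PP rate = p/(1 − f).

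| f avatrombopag | f placebo | Avatrombopag | Placebo | Difference (points) |
|---|---|---|---|---|
| 0 | 0 | 53.0% | 18.0% | 35.0 |
| 3% | 3% | 0.53/0.97 = 54.6% | 0.18/0.97 = 18.6% | 36.1 |
| 5% | 5% | 0.53/0.95 = 55.8% | 0.18/0.95 = 18.9% | 36.8 |
| 10% | 10% | 0.53/0.90 = 58.9% | 0.18/0.90 = 20.0% | 38.9 |
| 10% | 0 | 58.9% | 18.0% | 40.9 |
| 0 | 10% | 53.0% | 20.0% | 33.0 |

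The rate rises in every arm where f is above zero. With equal shares the difference is 35/(1 − f), which always exceeds 35. With unequal shares it can fall. For small shares this happens when 0.18 × f(placebo) exceeds 0.53 × f(avatrombopag), that is, when the placebo share is about 0.53/0.18 = 2.9 times the avatrombopag share or more.

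**Refusal criterion.** Let r be the share removed, assumed untransfused and unrescued and therefore scored as responders: PP rate = (p − r)/(1 − r).

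| r avatrombopag | r placebo | Avatrombopag | Placebo | Difference (points) |
|---|---|---|---|---|
| 5% | 5% | 0.48/0.95 = 50.5% | 0.13/0.95 = 13.7% | 36.8 |
| 10% | 10% | 0.43/0.90 = 47.8% | 0.08/0.90 = 8.9% | 38.9 |
| 0 | 5% | 53.0% | 13.7% | 39.3 |
| 5% | 0 | 50.5% | 18.0% | 32.5 |

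Both rates fall. A refusal needs an offer of platelets, and the planning non-response rates (82% v 47%) make an offer likelier on placebo, so the placebo rate probably falls more.

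**Both criteria at 5% in each arm.** 0.48/0.90 = 53.3% v 0.13/0.90 = 14.4%, difference 38.9 points. Avatrombopag hardly moves and placebo drops.

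**Scoring refusers in counts.** Take 33 placebo subjects with 6 recorded responders, 2 of them refusers, and avatrombopag at 53% with none:

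- Kept as recorded: 6/33 = 18.2%, difference 34.8 points.
- Excluded: 4/31 = 12.9%, difference 40.1 points.
- Kept as failures: 4/33 = 12.1%, difference 40.9 points.

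Rescoring refusers as failures in the PP set alone would therefore widen the difference further, and would give the same subject different outcomes in the two sets.

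**The case against.** There is an adherence argument for both criteria. Inclusion criterion 3 makes the need for platelets conditional on there being no clinically significant rise in count. Protocol 9.1.2.3 places the Visit 4 assessments before the procedure, and note g to Protocol Table 5 requires the hematology sample before any transfusion. Platelets given before the count is known cannot reflect the count response, and declining platelets does not show that none were needed.

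This stands in part for a prophylactic transfusion. It does not cover platelets given for bleeding, which the criterion also catches. Note g concerns taking the sample, not knowing its result. Such a subject also remains a failure by the endpoint definition, whatever the reason for the transfusion.

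The consequences are limited. The primary analysis uses all randomised subjects and counts missing outcomes as transfused. No success rule uses the PP set, and the other three listed sensitivity analyses do not depend on it. SAP 5.2.1 reports set sizes by treatment group, and SAP 5.2.3 has major deviations identified before unblinding. All of this stands.

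A reader might infer that both criteria discard failures and that the PP analysis therefore overstates response and benefit. The documents do not support that. Scored by platelets received, refusers are mostly responders, and removing them lowers response. The effect on the difference depends on counts and a split by arm that the documents do not give.

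**Conclusion.** The point holds in a limited form. Under the SAP's own definitions, and with no further assumption, the early-transfusion criterion removes only primary-endpoint failures when the transfusion follows randomisation. It raises the PP response rate in any arm where it applies: at the planning rates, by 2.8 to 5.9 points on avatrombopag and 0.9 to 2.0 on placebo for an assumed 5% to 10% removed. The refusal criterion lowers response, provided refusers are scored by receipt; SAP 5.3.2 and the CRF description imply this but do not state it.

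The bias in the treatment difference has no known sign. For early transfusion alone, the assumed shares give 33.0 to 40.9 points against 35.0. The FAS primary test and the power are not affected. The weakness is confined to one supportive analysis, but it is easily removed.

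**What to change.** In SAP 5.2.1, delete the early-transfusion criterion and keep those subjects in the PP set as non-responders, as in the FAS. At the least, state that it does not apply to platelets given for bleeding.

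In SAP 5.4.1, state one scoring rule for subjects who refuse a transfusion and use it in both the FAS and the PP set. Add the alternative scoring to SAP 5.4.1.1 as a sensitivity analysis. Report the number of early-transfused subjects and of refusers by arm within each baseline platelet cohort.

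The cost is SAP wording plus one short table and one extra sensitivity run. The PP set will include some subjects transfused without reference to their count, so keeping them makes PP response rates slightly lower than under the current list.

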5.2.2 Subject Disposition

Subject disposition will be summarized by treatment group for FAS and the Safety Analysis Set. The number (percentage) of subjects who completed or discontinued prematurely from the study and their reason for discontinuation will be summarized by treatment group. In addition, the number of subjects screened and the number and percentage of subjects who failed screening and the reasons for screen failure will be summarized, based on data recorded on the Screening Disposition CRF.

5.2.3 Protocol Deviations

Major protocol deviations will be identified, reviewed and documented by the clinical team prior to database lock/treatment unblinding. All protocol deviations will be categorized according to standard classifications including the following:

- Violations of inclusion/exclusion criteria
- Noncompliance with protocol procedures/assessments
- Noncompliance of drug dosage
- Use of prohibited treatments

All significant protocol deviations will be listed, and summarized by category and by treatment group.

5.2.4 Demographic and Other Baseline Characteristics

Demographic and other baseline characteristics for the FAS and Safety Analysis set will be summarized for each treatment group and overall using descriptive statistics or frequency count. Continuous demographic variables include age, weight, height and body mass index (BMI); categorical variables include age group (<65, and ≥ 65 years old), sex, ethnicity, race, region and country. The following baseline disease characteristics will also be summarized:

- Baseline platelet count and its category ($<40 \times 10^9/L$ and 40 to $<50 \times 10^9/L$)
- Bleeding risk associated with the elective procedure (low, moderate and high based on Amendment 02 categorization) and the type of elective procedure
- HCC status (yes and no) and Barcelona-Clinic Liver Cancer (BCLC) stage (0, A, B, C and D)
- Model for End-stage Liver Disease (MELD) score
- Child-Turcotte-Pugh (CTP) score and CTP grade (A, B and C)
- Baseline international normalized ratio (INR) and its category (≤ 1.6 and >1.6)
- Portal vein flow rate as per Doppler Sonography assessment
- Creatinine clearance and disease etiology.

MEDICAL HISTORY

All medical histories as documented by the Investigator will be coded using the Medical Dictionary for Regulatory Activities (MedDRA).

The number (percentage) of subjects reporting a history of any medical condition will be summarized by System Organ Class (SOC), preferred term for each treatment group and overall based on FAS.

5.2.5 Prior and Concomitant Therapy

All investigator terms for medications recorded on the CRF will be coded using the WHO Drug Dictionary (WHO DD).

Prior medications are defined as medications that stop prior to the first dose of study drug. Concomitant medications are defined as medications that (1) start before the first dose of study drug and are continuing at the time of the first dose of study drug, or (2) start on or after the date of the first dose of study drug, up to 30 days after the last dose of study drug.

The number (percentage) of subjects who take prior and concomitant medications will be summarized using the Safety Analysis Set by treatment group, Anatomical Therapeutic Chemical (ATC) Classification, and WHO DD preferred term. In addition, the number (percentage) of subjects who take the concomitant medications associated with elective procedures will also be summarized using the Safety Analysis Set by treatment group, ATC Classification, and WHO DD preferred term.

If a subject takes the same medications for the same class level or drug name, the subject will be counted only once for that class level or drug name.

5.2.6 Treatment Compliance

Treatment compliance is defined as follows:

$$\frac{\text{Total number of tablets dispensed} - \text{total number of tablets returned}}{\text{Total number of tablets subject should have taken}}$$

Treatment compliance will be summarized using descriptive statistics by treatment group based on FAS and Safety Analysis Set. Treatment compliance will also be summarized by treatment group using the categories <80%, ≥80% to ≤100%, >100% to ≤120%, and >120%.

5.3 DATA ANALYSIS GENERAL CONSIDERATIONS

The FAS will be used as the primary population for all efficacy analyses, while the PP will be used in supportive analyses of the primary efficacy endpoint and Safety analysis set will be used for all safety analyses. Unless stated otherwise, all efficacy analyses will be performed at $\alpha=0.05$ significance level and only descriptive statistics or frequency count will be generated for safety analyses without any hypothesis testing.

5.3.1 Pooling of Centers

This study is a multicenter international study with an estimated 100 centers participating in the study. Due to small expected number of subjects in each center, all analyses will be performed with all centers pooled across the study unless stated otherwise. Consistency of results across geographic regions will be examined as specified in the respective sections in this document.

5.3.2 Adjustments for Covariates

The primary efficacy endpoint, the proportion of subjects without platelet transfusion or any rescue procedure for bleeding, and the first secondary efficacy endpoint, proportion of subjects with platelet count $\geq 50 \times 10^9/L$ on Procedure Day, will be analysed separately within each

baseline platelet count cohort ($<40 \times 10^9/L$ or from 40 to $<50 \times 10^9/L$) using the Cochran-Mantel-Haenszel (CMH) test adjusting for the risk of bleeding associated with the elective procedure (low, moderate, or high based on Amendment 02 categorization). Since the HCC status is included in the randomization stratification for safety purposes only, not for efficacy consideration, HCC will not be included in the CMH model for the primary efficacy analysis.

5.3.3 Multiple Comparisons/Multiplicity

The primary efficacy endpoint will be tested between the individual avatrombopag treatment group (40 or 60 mg) and matching placebo within each baseline platelet count cohort ($<40 \times 10^9/L$ or from 40 to $<50 \times 10^9/L$), each at a significance level of $\alpha=0.05$. The primary efficacy endpoint is considered positive only if the tests are statistically significant for both baseline platelet count cohorts to control the family-wise Type I error rate at a significance level of $\alpha=0.05$.

A sequential gatekeeping testing procedure will be used for the secondary efficacy endpoints to control the family-wise Type I error rate at a significance level of $\alpha=0.05$. The secondary efficacy endpoints will be analyzed if the primary efficacy endpoint is statistically significant for both baseline platelet count cohorts. The first secondary efficacy endpoint is tested first within each baseline platelet count cohort, each at a significance level of $\alpha=0.05$. Only if the first secondary efficacy endpoint is statistically significant for both baseline platelet count cohorts, the analysis of second secondary efficacy endpoint will proceed within each baseline platelet count cohort, each at a significance level of $\alpha=0.05$. No alpha adjustment is planned for other efficacy endpoints.

5.3.4 Examination of Subgroups

Subgroup analysis of primary efficacy endpoint will be performed using age group (<65 and ≥ 65 years old), sex (male and female), race (white, black, Asian, and other), geographic region, bleeding risk associated with procedure (low, moderate, and high based on Amendment 02 categorization), MELD score (<10 , 10-14, and >14), and CTP grade (A, B, and C). Additional subgroup analysis may also be explored, if deemed appropriate.

5.3.5 Handling of Missing Data, Drop-outs, and Outliers

Unless stated otherwise, missing values will be considered as non-responders in responder analyses for all efficacy analyses; observed data will be used in other type of efficacy analyses. Details can be found in [Sections 5.4, Efficacy Analyses](#).

All safety analyses will be performed based on the observed data only.

5.3.6 Other Considerations

None

5.4 EFFICACY ANALYSES

The FAS will be used as the primary population for the efficacy analyses, while the PP will be used as a supportive analysis. All analyses of platelet counts will be based on local laboratory results.

5.4.1 Primary Efficacy Analyses

The primary efficacy variable is the proportion of subjects who do not require a platelet transfusion or any rescue procedure for bleeding after randomization and up to 7 days following an elective procedure.

The null hypothesis is that the proportion of subjects not requiring a platelet transfusion or any rescue procedure for bleeding after randomization and up to 7 days following an elective procedure is the same between the avatrombopag and placebo treatment groups. The corresponding alternative hypothesis is that the proportion of subjects not requiring a platelet transfusion or any rescue procedure for bleeding after randomization and up to 7 days following an elective procedure is not the same between avatrombopag and placebo. This hypothesis will be tested separately with each baseline platelet count cohort.

The proportion of subjects not requiring a platelet transfusion or any rescue procedure for bleeding will be tested between the individual avatrombopag treatment group (40 or 60mg) and matching placebo within each baseline platelet count cohort ($<40 \times 10^9/L$ or from 40 to $<50 \times 10^9/L$), each at a significance level of $\alpha=0.05$ using the generalized Cochran Mantel Haenszel (CMH) test adjusting for the risk of bleeding associated with the elective procedure (low, moderate, or high based on Amendment 02 categorization).

- For subjects with platelet count $<40 \times 10^9/L$ at baseline, the treatment comparison will be carried out between the 60 mg avatrombopag treatment group (Group A) versus matching placebo (Group B).
- For subjects with platelet count from 40 to $<50 \times 10^9/L$ at baseline, the treatment comparison will be carried out between the 40 mg avatrombopag treatment group (Group C) versus matching placebo (Group D).

This study will be considered as positive if statistical significance is achieved for primary efficacy endpoints for both baseline platelet count cohorts.

The 95% CI for the proportion of subjects not requiring a platelet transfusion or any rescue procedure for bleeding will be calculated for each treatment group within each baseline platelet count cohort. In addition, the 95% CI for the difference between avatrombopag and matching placebo will also be provided within each baseline platelet count cohort using normal approximation method.

Since the HCC status is included in the randomization stratification for safety purposes only, not for efficacy consideration, HCC will not be included in the CMH model for the primary efficacy analysis.

Subjects with missing information about the primary efficacy outcome due to early withdrawal or other reasons will be considered as having received a transfusion for the primary analysis.

